Saliva, the bulk fluid of the oral cavity is very important in maintaining the functions and balance in the oral cavity including candidiasis and enamel erosion prevention. In past studies, residual mucosal fluid levels were seen to vary in different oral cavity sites from an average of $70-100~\mu m$ (2)(3). In addition, the vault of the hard palate has much less mucosal fluid thickness than the floor of the mouth. Over the moisture layer is the lipid layer and reduction or loss of this

moisture layer can contribute to the subjective perception of the dryness in the mouth. An addition of the lipid layer will also increase lubrication in the oral cavity.

Unstimulated salivary flow in dry mouth patients has shown an increased clinical oral dryness score and mucosal wetness is at a significantly reduced rate (p<0.05) when compared with healthy subjects (4).

Historically, various products containing methylcellulose, water, oily emulsions etc., have been used to alleviate the subjective sensation of dryness in the oral cavity in the forms of rinse, gel, ointment and paste. However, the alleviation of the dry mouth symptoms has been varied.

This study will investigate a semi solid cohesive gel (referred to as Whitening Gel) that has the primary marketed purpose of teeth whitening. We theorize that the whitening gel's retention in the oral cavity is longer than rinse forms and this is likely to promote the flow of saliva by stimulating taste buds which could alleviate the sensation of dryness in the oral cavity.

The study product contains an inert hydrophobic phase in an amount from 30% to 98%, preferably from 40% to 90% by weight of the composition. It also contains an emulsifying system in an amount from 1% to 10%, preferably from 3% to 7% by weight of the composition.

P&G's whitening gel emulsifying system is comprised of at least one surfactant having an hydrophilic-lipophilic balance (HLB) <10, preferably comprised between 3 and 7, and at least one surfactant with HLB>10, preferably comprised between 12 and 16.

The optimal duration and frequency of application for whitening is up to 4 times a day. For the purpose of this study, the whitening gel will set on the subject's teeth for 5 minutes during each use.

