The product being used is a commercially available product, known as "Crest Whitening Emulsions", will be used as the investigative product. There will be no active control group. This is not the first time P&G whitening gel will be used in humans. We do believe this is the first study investigating dry mouth sensation from using a whitening gel.

- III) Research Plan
 - A) Experimental Design

This will be a single center, two visit study investigating the effectiveness of dryness in the oral cavity, whiteness of teeth, and teeth sensitivity after one week's use of whitening agent.

B) Sample Size and Statistical Analysis

Sample size

This is a single site study. All study-related procedures will take place at TUSDM. Based on our preliminary data from a previous study, we anticipate 25 subjects will be needed to achieve the necessary statistical power required to observe expected differences in relief of dryness in the oral cavity. Because we anticipate the potential of many screen failures due to the VAS scale and saliva production requirements outlined in the exclusion/inclusion criteria section, we will screen/enroll a total of 100 subjects to conservatively account for potential dropouts or screening failures.

Statistical analysis

The subjects will be asked to complete one questionnaire each visit. Completing the first part before the application of the study product, and completing the second part after the application of the study product, as directed on the questionnaire. The self-reported scores from the visual analogue scales (VAS) will be considered on the first and final visit. The salivary flow before and after the application of the product, Pre & Post-Product Use Dry Mouth & Sensitivity Questionnaire before and after the product application will be compared using a student -t test method. The same method will be used to make comparisons of these gathered data points between the first and final visits.

Randomization

This will be an open label study; thus no randomization plan is necessary.

Blinding

There will be no blinding for this study.

C) Products

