- 11. Photographs of subject teeth will be taken by a standard dental camera. The photos will only contain subject teeth and oral cavity with no subject identifiers visible. In addition to the ICF, the subjects will be asked to sign a photo release form. If the subject does not wish to sign this form, their photographs will not be taken. Those who do not consent to having their photos taken will be tracked in the enrollment log. Photographs will be taken pre-application of the study product at visit 1.
- 12. Distribution of study product and diary: One box of study whitening gel product, (0.88Oz) toothpaste, and a toothbrush will be dispensed by study team members. This is to ensure all participants are using the exact same dental products during the trial period. The subjects will be asked to not use any other oral tools or products during the trial period aside from the ones distributed by the study team at Visit 1. A diary will also be dispensed for the record keeping of the application of the products. A study team member will again verbally tell the participant the instructions that are provided with the study product and that per the

instructions, they can apply the product up to 4 times per day until their next study visit. The same script from step 9.a. will be used.

13. Gift card will be distributed upon successful completion of visit.

Visit 2 (1-1.5 hours) Final Visit - 7 ∓ 2 days after visit 1

- 1. Subject will be called 1-2 days before their appointment to confirm that in order to participate, they must:
 - a. Not consume alcohol for 24 hours prior to their visit.
 - b. Not brush their teeth for 1.5 hours prior to their visit.
 - c. Not have had anything to eat or drink (including chewing gum or eating candy) for 1.5 hours prior to their visit). Water is acceptable to drink up to 1 hour prior to the study visit.
 - d. Not smoke 1.5 hours prior to their visit.
- 2. Medical history will be reviewed, and any changes will be noted. Any changes to medications will also be reviewed and noted.
- 3. Eligibility and subject withdrawal criteria will be reviewed to ensure the subject still qualifies for the study.
- 4. Subject medications with potential side effects being dry mouth will be verified using the Physician's Reference Desk. Subjects will be asked to confirm that they have taken their medications as prescribed since Visit 1.

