- An oral exam, including evaluation of oral cavity, soft and hard tissues, will be completed following standard of care procedures in US dentistry using a mouth mirror and dental explorer.
- 6. Saliva Collection 1 (pre-product application): Saliva will be collected using the drooling method for 5 minutes into a pre-weighed vial. The post collection weight will be subtracted from the pre-weight to determine the flow rate. The saliva samples will be discarded after they are weighed.
- 7. The paper questionnaire will be given to subject to complete before application of study product and after application of study product. The questionnaire

- includes the Visual Analogue Scale (VAS) questionnaire on dry mouth, quantity of saliva, and perceived sensitivity of teeth.
- 8. Application of study product: A study team member will ask the subjects to apply the gel to their teeth. Subjects will then be asked to sit for 5 minutes to allow the gel to set on their teeth.
- 9. Saliva Collection 2 (post-product application): Saliva will be collected using the same drooling method as Saliva Collection 1. The saliva samples will be discarded after they are weighed.
- 10. Photographs of subject teeth will be taken by a standard dental camera. The photos will only contain subject teeth and oral cavity with no subject identifiers visible. Photographs will be taken post-application of the study product at visit 2.
- 11. The study diary and any leftover whitening gel product will be collected.
- 12. Gift card will be distributed upon successful completion of visit.

	Screening/ Baseline Visit Day 0	Visit 2 Day 7 (±2 days)
Informed Consent Form	X	Day 7 (±2 days)
Demographics	X	
Collect and/or Review Medical History	X	Х
Review eligibility and withdrawal criteria		Х
Confirmation of Xerogenic Medications	Х	
Pre-Product Use Dry Mouth & Sensitivity	Х	Х
Questionnaire		
Post-Product Use Dry Mouth & Sensitivity	x	Х
Questionnaire		
Unstimulated Salivary Test	x	Х
Oral Exam	x	Х
Evaluate eligibility criteria	x	
Oral Photographs	X (Pre-Application)	X (Post-Application)
Demonstration of Product Use	х	
Product Usage	X	X

Post Product Use Unstimulated Salivary Test	х	х
Product Distribution or Collection	X	X
Adverse Event Reporting (if applicable)	Х	Х
Stipend	Х	Х

G) Subject Safety

1) Adverse Event Reporting

Adverse Events

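### The between-visit change can combine a recent home dose with a week's use without the plan saying which is measured, and post-application vial weight counts any gel as saliva

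*Combined protocol and SAP*

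**What the plan says.** **Home use and Visit 2 readings.** Section III.F, Visit 1 step 12, tells subjects that "they can apply the product up to 4 times per day until their next study visit". The Visit 2 call list (step 1) restricts alcohol, brushing, food and drink, and smoking. Its food item reads "Not have had anything to eat or drink (including chewing gum or eating candy) for 1.5 hours prior to their visit". The study gel is not on the list. Step 6 at Visit 2 is "Saliva Collection 1 (pre-product application): Saliva will be collected using the drooling method for 5 minutes into a pre-weighed vial"; the first part of the questionnaire is also completed before the in-clinic application at step 8. For the diary, Visit 1 step 12 says "A diary will also be dispensed for the record keeping of the application of the products", and Visit 2 step 11 says "The study diary and any leftover whitening gel product will be collected".

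**Target and analysis.** Section III.A describes the outcomes as dryness, whiteness and "teeth sensitivity after one week's use of whitening agent". Section III.B plans t tests before and after application, then adds: "The same method will be used to make comparisons of these gathered data points between the first and final visits". Section II theorises that the gel's "retention in the oral cavity is longer than rinse forms and this is likely to promote the flow of saliva".

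**Post-application saliva.** At both visits the subject applies the gel, sits for 5 minutes, and then drools into a pre-weighed vial. Flow rate is derived from the change in vial weight. The protocol text describes no removal step and no correction for gel. Section I.A lists objective improvement of saliva production as a secondary aim.

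**The concern.** The pre-product label covers two different conditions. At Visit 1 no study gel has been used. At Visit 2 the last home dose may have been minutes or many hours earlier. The protocol controls other oral exposures before measurement but leaves out the one under test, and its own rationale expects that exposure to persist and to stimulate saliva. The VAS item used for eligibility (section III.D) asks about dryness at the moment of answering, so a short-lived effect can move it.

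A lower dryness score at Visit 2 could therefore be credited to a week of use when part or all of it reflects a recent dose. This reaches the primary outcome.

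The vial problem is separate and concerns a secondary outcome. Gel that reaches the vial can only add weight, so any error in the within-visit comparison runs in the hoped-for direction.

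**Working it through.** **Plan's own figure.** Section III.B gives 25 subjects but no effect size, SD, significance level or power, so that number cannot be reproduced. It is used below only to judge what a time-since-use analysis could show.

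**1. Between-visit change.** Let W be the effect of a week's use apart from any dose still acting, f the share of subjects with a dose still acting at the Visit 2 pre-product reading, and A the mean effect of such a dose.

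- Expected change in the pre-product reading = W + f × A, before the other influences that an uncontrolled comparison cannot exclude.
- If f = 0, the change reflects W. If f > 0 and A is not zero, it reflects both.
- The documents give neither f nor A, so no size can be computed.
- The trial does collect information on A: the Visit 1 pre/post change is measured before any home dose. It does not show how fast the effect fades, nor how many subjects dosed shortly before Visit 2. For flow, it also carries the vial problem below.
- f can be approached only through the time of last use. The protocol text does not ask for it at Visit 2, and the diary form is not in the documents.

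What 25 subjects can show about time since last use (Fisher z, two-sided 5%, 80% power):

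- detectable correlation = tanh((1.960 + 0.842) / √(25 − 3)) = tanh(0.597) = 0.535, about 0.54.

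Only a strong relation would be detected, so such an analysis should stay descriptive.

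**2. Gel in the vial.** Inputs: ceiling of 0.18 mL/min (section III.D); 5-minute collection (section III.F); dose of about ½ tsp (section III.C). Assumptions: 1 US tsp = 4.93 mL, so ½ tsp = 2.464 mL; gel and saliva both at 1 g/mL.

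- Saliva at the ceiling: 0.18 × 5 = 0.90 mL, about 0.90 g.
- Gel weight that reads as a 10% rise: 0.10 × 0.90 = 0.090 g.
- Share of one dose: 0.090 / 2.464 = 3.7%.

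| Baseline flow (mL/min) | Saliva in 5 min (g) | Gel reading as +10% (g) | Share of ½ tsp |
|---|---|---|---|
| 0.18 (ceiling) | 0.90 | 0.090 | 3.7% |
| 0.10 (assumed) | 0.50 | 0.050 | 2.0% |
| 0.05 (assumed) | 0.25 | 0.025 | 1.0% |

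With gel density between 0.85 and 1.1 g/mL, the 3.7% becomes 4.3% to 3.3%. These are break-even figures: they say how much gel would matter, not how much is present.

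**The case against.** The strongest reply is that effect under use is the natural target. Subjects may use the gel until the visit, and no section claims an effect that outlasts dosing. On that reading a recent dose is part of the effect and not bias. This stands as far as it goes: the target is legitimate. But the phrase about one week's use fits either meaning, and a report on this plan would not tell readers which was measured.

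A reader might infer that the pre-product label contradicts the permission to use the gel up to the visit. It does not. By the order of the steps it plainly means before the in-clinic dose, and nothing promises a gel-free reading.

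A reader might also infer that the recent-dose effect cannot be gauged at all. That is too strong, because the Visit 1 pre/post readings estimate its immediate size. The diary may already hold the time of last use.

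On the vial, section II calls the gel semi-solid and cohesive, which may keep the share reaching the vial small. The product packet, which supplies the application script, is not in the documents and may cover removal. Section II also says the gel sets for 5 minutes at each use, which could imply limited contact, though it does not say that the gel is then removed. Nor is 0.9 mL a cap on every collection: 0.18 mL/min is a baseline eligibility limit, and flow after application may be higher.

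These points limit the size of the concern. They do not supply the missing statement of target or a handling rule for gel weight.

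**Conclusion.** The concern holds in two limited parts.

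First, the between-visit change in dryness VAS and flow can combine a recent-dose effect with a one-week effect, and the plan does not say whether the state under ongoing use is what it measures. The size is unknown. The documents do not show that subjects will dose shortly before Visit 2, so it would be wrong to say that those readings are contaminated.

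Second, any gel reaching the post-application vial is counted as saliva and biases the within-visit comparison upward. At the baseline ceiling, about 0.09 g (3.7% of a ½ tsp dose at an assumed 1 g/mL) reads as a 10% rise, and less suffices at lower flows. The documents do not support saying that an observed rise would be gel and not saliva.

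Both parts should be addressed, because following the plan as written can credit a recent dose to a week of use and gel weight to saliva production. Confidence is medium, since the diary, questionnaire and packet were not available.

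**What to change.** 1. In sections III.B and III.F, state that Visit 2 pre-product readings are taken before the in-clinic dose, and whether they represent the state under ongoing use. Whether any interval since the last dose applies is for the sponsor and investigator to decide. Record the time of last application at Visit 2 unless the diary already captures it. Report the between-visit VAS and flow changes descriptively by time since last use, alongside the Visit 1 pre/post change as the in-trial estimate of the acute effect.

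2. Keep the planned within-visit weight comparison, but report the post-application weight as total expectorate (saliva plus any gel). Do not conclude improved saliva production from it alone. Read it with the pre-application weights at Visits 1 and 2, bearing in mind that the Visit 2 weight may follow a recent home dose.

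**Cost.** One clarifying sentence, at most one recorded field, one relabelled outcome and one descriptive table. The downside is a weaker claim from the within-visit flow comparison. The other limits of an uncontrolled, open-label comparison remain.

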The investigational product to be used in this study is manufactured by P&G and called, "Crest Whitening Emulsions". The amount of each dose should be enough to cover the entire tip of the whitening wand, approximately ½ a tsp. The use of the study product in this study will be for what they are approved for. Per the manufacturer's instructions, study subjects will be asked to apply the study product up to 4 times a day.

Procter and Gamble will be supplying the study product gel to the study team. IDS will not be involved in this study.

The investigative product to be used in this study is a hydrophobic emulsion containing agent (a teeth whitening gel with emulsification gel). It contains:

Petrolatum, Water, Hydrogen Peroxide, Flavor, Sucralose, Sorbitan Palmitate

D) Subject Characteristics

- 1) Inclusion Criteria
 - At least 18 years of age.
 - The inability to produce more than < 0.18mL/min of unstimulated saliva.
 - Score of 5 or more on question 1 of the VAS dry mouth scale (How severe is your dryness right now?), evaluated in the Pre-Product Use Dry Mouth & Sensitivity Questionnaire .
 - Evidence of currently taking Xerostomia-inducing medication such as, antihypertensives, anti-anxiety agents, psychiatric remedies, antihistamines.
 - Subject not currently using any teeth whitening or desensitizing products
 that contain potassium nitrate such as Sensodyne or Pronamel.
 - Subject willing to comply with the study regimen and products.

2) Exclusion Criteria

- Subjects who are currently pregnant (self-reported).
- Subjects able to produce more than 0.18mL/min of unstimulated saliva

- Subjects that have ever received therapeutic radiation in the head and neck area.
- Subjects with a diagnosis of conditions that would affect salivary flow such as Sjogren's Syndrome.
- Subjects with a condition the investigator believes not suitable for the study such as autoimmune diseases that impact salivary flow.
- Subjects that currently use whitening toothpaste, desensitizing toothpaste, or any other products causing similar results.
- Subjects currently participating in any other research studies.
- Subject unable to provide consent (ex. Cognitively impaired adults).
- Non-English speaking

3) Subject Withdrawal/Termination Criteria

- Subjects who do not comply with the study procedures, such as use of teeth whitening products, may be withdrawn from the study.

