- The study team may terminate subjects if they no longer fulfill inclusion criteria, if an exclusion criterion is met, or if they do not show up for scheduled study visits.
- Subjects who experience an unanticipated adverse drug effect will be withdrawn from the study.
- Subjects unable to complete the study procedures due to a medical condition such as dry mouth and sensitivity conditions that result in the inability to capture meaningful data during the study procedures.
- Subjects may choose to withdraw from the study at any time.

Subjects may remain patients of TUSDM if they decide to withdraw from the study or are withdrawn by the study team.

If during the course of their participation in the study, a subject chooses to withdraw or is withdrawn by the research team, any data that has been

collected will not be included in the analysis and the subject will be asked to return any leftover whitening gel and the diary. The subject is able to keep the toothpaste and toothbrush.

Subjects will not be able to partially withdrawal from study intervention and just be involved with continued data collection.

The Principal Investigator will determine whether subjects (either withdrawn subjects or subjects completing the study) are in need of additional treatment and/or follow-up observation as a result of participation in this trial and will refer them to their primary care provider for further care. Subjects and/or their insurance will be responsible for the cost of any standard of care follow-up visits or additional treatment that is not part of this study.

4) Vulnerable Populations

Transgender subjects will be recruited as part of this study. All subjects will be asked on the Medical/Dental History Form to identify their sex, to which they will answer however they choose. They will not be sought out or targeted for participation and will not be discriminated against as a result of their sexual orientation/gender identity. The subjects will not be asked to disclose if they are transgender or not on the Medical/Dental History Form.

Cognitively impaired adults and pregnant adults will not be enrolled in this study. There would be no direct benefits to these specific vulnerable populations by enrolling them. Pregnancy will be determined through self-reporting.

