If the participant indicates they may be interested in participating after going through the consent form with the investigator, and the investigator determines the participant has the capacity to provide informed consent, the participant will be asked to provide informed consent at that time. Written consent will be obtained following "SOP: Written Documentation of Consent (HRP-091)" and we will follow the "SOP: Informed Consent Process for Research (HRP-090)." Patients will certify their willingness to participate in the study by signing and dating the IRB approved informed consent document. The subject will be given a copy of the consent form.

If any new finding requires any change to the informed consent form, the subject will be reconsented.

Study Location:

Tufts University School of Dental Medicine

3) Personnel

All study personnel will be GCP and CITI certified and trained on all their roles, responsibilities, and study procedures.

- I. Ongoing communication with the IRB and sponsor—The PI
- II. **Subject Recruitment** The PI or his representative
- III. **Obtaining Informed Consent** The PI, Co-I, or a study coordinator, who is CITI and GCP trained, will obtain informed consent.
 - a. The PI or CO-I will be available to answer any medical questions the subject may have.
- IV. Conducting inclusion/exclusion evaluation the PI or CO-I
- V. Saliva collection, questionnaire dissemination, product use demonstration and dissemination The PI or his representative
- VI. Maintaining participant's research records The PI
- VII. Monitoring and reporting of adverse events The PI
- 4) Payment for Participation
 - (a) Compensation

Subjects will be given a \$75 Target gift card upon successful completion of each study visit. In total, subjects will receive \$150 for their full participation in the study, as long as they attend both visits and are not withdrawn. Subjects that withdraw before either study visit is completed will not be provided a parking voucher. Subjects who fail to meet the inclusion criteria of the study will receive a \$25 Target gift card.

(b) Transportation

Travel reimbursement and transportation costs.
 Subjects will be provided a parking voucher to accommodate their parking needs at TUSDM at the successful completion of each study visit.

(c) Costs and Insurance

Neither the subject, nor their insurance company, will be billed for any study procedures.

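### The Visit 2 payment depends on not being withdrawn, while disclosing an unanticipated adverse effect or use of another product can lead to withdrawal before payment: a disincentive to report

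*Combined protocol and SAP*

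**What the plan says.** Section III.H.4(a) gives each subject a $75 "Target gift card upon successful completion of each study visit". The $150 total is paid "as long as they attend both visits and are not withdrawn". A screen failure receives $25. Section III.H.4(b) ties the parking voucher to successful completion of each visit. Section III.F, Visit 2, step 12 repeats the rule for the card: "Gift card will be distributed upon successful completion of visit".

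Section III.D.3 sets the grounds for withdrawal:

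- Mandatory: "Subjects who experience an unanticipated adverse drug effect will be withdrawn from the study".
- Discretionary, for non-compliance: "Subjects who do not comply with the study procedures, such as use of teeth whitening products, may be withdrawn from the study".
- Discretionary, for eligibility: "The study team may terminate subjects if they no longer fulfill inclusion criteria, if an exclusion criterion is met".
- Inability to complete procedures because of a medical condition, for example "dry mouth and sensitivity conditions that result in the inability to capture meaningful data during the study procedures".

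Section III.F, Visit 1, step 12 adds: "The subjects will be asked to not use any other oral tools or products during the trial period", apart from those supplied. Section III.D.2 excludes current users of whitening or desensitizing toothpaste or similar products, and III.D.1 requires current use of a xerostomia-inducing medication.

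**The concern.** The study is single-arm and open label, and the subject uses the gel unsupervised for about a week. Symptoms that resolved before Visit 2, use of other oral products, and medication changes reach the study team mainly because the subject mentions them. These are the disclosures that can lead to withdrawal, and withdrawal costs the subject the second payment. The payment rule thus works against the safety and adherence reporting that the plan relies on.

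Section III.D.3 also removes a withdrawn subject's data from the analysis. A disclosure that triggers withdrawal therefore takes that subject out of the efficacy data too, and a trigger left undisclosed keeps the subject in.

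**Working it through.** **1. The plan's own figure.** Two visits at $75 each: 2 × 75 = $150, which matches III.H.4(a).

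**2. What is at stake at Visit 2.** The Visit 1 card is handed over at Visit 1 step 13 and is kept. The loss is 150 − 75 = $75, or 75/150 = 50% of the total, plus the Visit 2 voucher. For that visit the withdrawn subject receives $0, whereas a screen failure receives $25 for Visit 1.

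**3. Order of events at Visit 2 (III.F).**

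| Step | Content |
|---|---|
| 2 | Medical history and medication changes |
| 3 | Review of eligibility and withdrawal criteria |
| 4 | Xerogenic medications verified, adherence to medication confirmed |
| 5 to 11 | Oral exam, saliva, questionnaire, gel, photographs, returns |
| 12 | Gift card |

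A subject withdrawn at step 3 cannot carry on for data collection alone, because III.D.3 rules out partial withdrawal. The visit is then not completed. On either condition, successful completion or not being withdrawn, the second card is not earned. No section of the protocol provides payment to a subject who attends and is withdrawn for safety or after an honest report.

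**4. Which disclosures can trigger withdrawal.**

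| Disclosure | Rule in III.D.3 | Trigger? |
|---|---|---|
| Unanticipated adverse drug effect | will be withdrawn | Yes, mandatory |
| Another whitening or desensitizing product | may be withdrawn | Yes, discretionary |
| Xerogenic medication stopped (inclusion criterion lost) | may be terminated | Yes, discretionary |
| Irritation, bleaching or sensitivity, listed as standard risks in III.E.1 | only if procedures or meaningful data are prevented | Not by itself |
| Skipped applications | use is up to 4 times a day, no minimum stated | Not clearly |

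**5. Illustration of under-reporting.** The documents give neither an event risk nor a reporting rate, so both are assumed here. With n = 25 subjects, true risk p and reporting probability r, the chance of at least one reported event is 1 − (1 − p·r)^25.

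| p | r = 1 | r = 0.75 | r = 0.5 |
|---|---|---|---|
| 5% | 72% | 62% | 47% |
| 10% | 93% | 86% | 72% |

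This shows how sensitive a study of 25 is to lost reports. It does not estimate the effect of the payment rule.

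**The case against.** The strongest reply is that the link is narrow. Mandatory withdrawal covers only unanticipated drug effects. The effects most expected of a whitening gel are listed as standard risks, the product is already marketed, and withdrawal on the other grounds is optional. Self-report is also not the only source: Visit 2 has an oral exam, sensitivity is scored on the questionnaire, and leftover gel is collected. Payment depends on completion, and nothing in the documents shows that subjects would withhold information. The consent form is not among the documents available and could contain other payment terms.

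Most of this stands, and it rules out several stronger readings:

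- A reader might infer that reporting any adverse effect costs the card. III.E.1 read with III.D.3 does not support that.
- A reader might infer that missed use costs the card. With a maximum frequency and no minimum, a skipped application is not clearly a breach.
- A reader might infer that the plan pays subjects for silence, or that it has no other source of information. The payment text shows no such intent, and the exam, questionnaire and returned gel are partial checks.

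The reply does not remove the core. Discretion still puts the money at risk. The term unanticipated adverse drug effect is not defined; III.G.1 defines an unanticipated problem and an unanticipated device effect, and both turn on severity and on frequency or incidence as well as nature. A subject cannot readily tell which symptoms would count. An exam cannot show a resolved symptom or use of another product, and the protocol does not say that returned gel is weighed.

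**Conclusion.** The concern holds in a limited form. As written, a subject who attends Visit 2 and discloses an unanticipated adverse drug effect must be withdrawn. One who discloses another whitening or desensitizing product, or a lost eligibility criterion, may be. Either can then lose $75 of $150 and the voucher before payment is made. That is a financial disincentive to report.

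The amount at stake follows directly from the text. The effect on reported event counts or adherence cannot be estimated from the documents, so no under-reporting rate should be attached to the point. The conclusion assumes that the withdrawal review is carried out in the stated order and that the consent form adds no separate payment for withdrawn subjects. The point deserves correction because the remedy is cheap and touches only the payment terms.

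**What to change.** 1. In III.H.4(a), delete the condition about not being withdrawn. State that each enrolled subject who attends a visit receives the $75 card and the parking voucher, whatever is decided about withdrawal at that visit. Bring the voucher sentence in the same paragraph into line.
2. Give the same payment to a subject withdrawn for an adverse effect reported before Visit 2, when the leftover gel and diary are returned, as III.D.3 already asks. Payment by attendance alone would still penalize prompt reporting during home use and favor waiting until Visit 2.
3. Change Visit 2 step 12 and III.H.4(b) from successful completion to the same rule, and align the consent form.
4. Keep the $25 screen-failure payment. Leave the clinical withdrawal rules as they are.

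Cost: a short formal amendment with IRB approval (section L), possibly re-consent of subjects already enrolled, and about $75 plus a voucher per affected subject. If 1 to 5 subjects were affected (an assumed range), the cards would cost 1 × 75 = $75 to 5 × 75 = $375. The downside is that some non-compliant subjects will be paid.
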